# 1.3 Summary of Key Safety Information for Study Drugs

Enzalutamide has been approved by the FDA, the EMA and Japan MHLW for metastatic CRPC. Worldwide, enzalutamide has been approved for the treatment of metastatic CRPC in more than 100 countries. Enzalutamide has also been approved for nonmetastatic CRPC in the US, EU and Japan as well as in more than 60 countries. In Dec 2019, enzalutamide was approved for the treatment of metastatic CSPC in the US (also referred to as mHSPC) and a marketing application for this indication is currently in review in the EU.

The safety profile of enzalutamide in subjects with CRPC is derived primarily from 5 phase 3 studies. Study CRPC2 (AFFIRM) was a randomized, double-blind, placebo-controlled, efficacy and safety clinical study of enzalutamide (160 mg daily) in 1199 subjects with progressive metastatic CRPC (mCRPC) previously treated with docetaxel-based chemotherapy. Study MDV3100-03 (PREVAIL) was a multinational, randomized, double-blind, placebo-controlled, efficacy and safety clinical study of enzalutamide in 1717 chemotherapy naïve subjects with mCRPC who have failed ADT. Study 9785-CL-0232 (Asian PREVAIL) was similar to PREVAIL except in an Asian population of 388 subjects. Study MDV3100-14 (PROSPER) was a randomized, double-blind, placebo-controlled, efficacy and safety clinical study of enzalutamide (160 mg daily) in 1401 subjects with nonmetastatic CRPC at high risk of disease progression based on baseline prostate-specific antigen (PSA) level and short PSA doubling time.

An analysis of 5 pooled phase 3 studies (AFFIRM, PREVAIL, Asian PREVAIL, PROSPER and ARCHES) indicated that the most frequently reported treatment-emergent adverse events (TEAEs) reported in  $\geq 10\%$  of patients in the enzalutamide group (n = 3371; enzalutamide dose; 160 mg/day) were:fatigue, back pain, nausea, hot flush, constipation, arthralgia, decreased appetite, diarrhea, hypertension, asthenia, fall, pain in extremity, musculoskeletal pain and headache. With the exception of nausea and pain in extremity, each of these events occurred in the pooled phase 3 enzalutamide group with a  $\geq 2\%$  higher incidence than in the placebo group (n = 2472). Only 2 TEAEs showed a higher rate in the enzalutamide vs the placebo group (event rate per 100 patient-years of treatment): fall (8.9% enzalutamide vs 4.6% placebo) and hypertension (8.2% vs 5.5%).

- CONFIDENTIAL -

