Lastly, the primary efficacy analysis in ARCHES demonstrated a statistically significant, robust and substantial improvement in radiographic progression-free survival together with clinically meaningful improvements in the key secondary endpoints of time to PSA progression, time to start of a new antineoplastic therapy, PSA undetectable rate and objective response rate and a trend in OS (observed at the time of interim analysis) in favor of enzalutamide plus ADT versus placebo plus ADT treatment. For the secondary endpoints, the ARCHES study demonstrated that enzalutamide prolonged the time to the first symptomatic skeletal event and time to castration-resistance. Assessments of patient-reported outcomes data showed that patients receiving enzalutamide plus ADT in ARCHES had a high baseline level of quality of life, which was maintained over time.

Based on the safety information collected to date in clinical trials and in commercial use, the safety profile experienced by patients remains consistent with the approved product label as well as events that can be seen in patients with prostate cancer. The safety profile in mHSPC patients in this study is expected to be consistent with the established safety profile for enzalutamide. To date, there are 4 important identified risks associated with enzalutamide (seizure, fall, nonpathological fracture and ischemic heart disease). While serious adverse events (SAEs) such as seizure have occurred in patients receiving treatment with enzalutamide, these events have been rare. To mitigate the risk of seizure, subjects with a history of seizure or any condition that may predispose to seizure (e.g., prior cortical stroke or significant brain trauma, brain arteriovenous malformation) are excluded from the trial. Study drug discontinuation is required for subjects experiencing either seizure or PRES. In addition to these patient exclusion and discontinuation requirements, the study design includes safety labs, scans and guidance related to concomitant medications to minimize the risks associated with enzalutamide and ensure timely intervention if needed.

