#### 6.3 Treatment Emergent Adverse Event (TEAE)

A TEAE is defined as an AE that occurs or worsen at any time during the treatment emergent period. The treatment emergent period is time interval encompassing the double-blind treatment emergent period and the OLE treatment emergent period.

The double-blind treatment emergent period is defined as the time interval from the first double-blind study drug intake up to 30 days after the date of the last dose of double-blind study drug, study discontinuation, the start of new antineoplastic therapy, or the first dose of OLE treatment, whichever occurs first.

If AE start date is the same date as the study start, then it will be considered as a TEAE if the box 'Onset after first dose of study' is ticked in the Electronic case report form(eCRF). If a patient experiences an event both during the pre-investigational period and during the investigational period, the event will be considered as TEAE only if it has worsened in severity (i.e. it is reported with a new start date).

The OLE treatment emergent period is defined as the time interval from the OLE study drug intake up to 30 days after the date of the last dose of OLE study drug, study discontinuation, or the start of new antineoplastic therapy, whichever occurs first.

AE with both a missing start and stop dates, and AEs with a missing start date but has a known stop date which is on or after the first dose of study drug will be considered treatment-emergent.

For each treatment group, the treatment emergent period is as follows;

- Enzalutamide group: from the first DBT study drug intake up to 30 days after the date of the last dose of study drug, study discontinuation, or the start of new antineoplastic therapy, whichever occurs first.
- Placebo group: from the first DBT study drug intake up to 30 days after the date of the last dose of placebo, start of open-label enzalutamide, study discontinuation, or the start of new antineoplastic therapy, whichever occurs first.
- Placebo crossover group: from the first OLE study drug intake up to 30 days after the date of the last dose of OLE study drug, study discontinuation, or the start of new antineoplastic therapy, whichever occurs first.

AEs will be coded to System Organ Class (SOC) and preferred term using MedDRA v23.0 and severity graded using National Cancer Institute's Common Terminology Criteria version 4.03 (NCI-CTCAE v4.03) for AEs.

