The number and percentage of patients with TEAEs, as classified by SOC and preferred terms will also be summarized by maximum severity (reported according to NCI-CTCAE version 4.03).

In the patient count, if a patient has multiple TEAEs with the same SOC or PT, but with different severity, then the patient will be counted only once with the worst severity. However, if any of the severity values are missing then the patient will be counted only once with missing severity. In the AE count, the AEs will be presented in each category they were classified to. Summaries will be provided for:

- TEAEs by NCI- CTCAE
- drug related TEAEs by NCI- CTCAE,
- serious TEAEs by NCI- CTCAE

The number and percentage of patients with TEAEs that equal to or exceed a threshold of 5.0% in any treatment group, classified by preferred terms (by decreasing frequency within the enzalutamide group) will be summarized by treatment group and time interval. The percentage of patients are calculated based on the number of patients still on treatment at the time-point corresponding to the lower limit of the time intervals. Time intervals will be categorized according to the following categories:

- $\leq$ 3 months;
- >3 months to  $\leq 6$  months;
- >6 months to  $\leq 12$  months;
- >12 months to  $\leq$ 24 months;
- >24 months to  $\leq$ 36 months;
- >36 months.

To adjust for the treatment duration, the number of TEAEs per 100 patients-years will be summarized, as classified by SOC and PT, per treatment group and CTI-CTC grade (3-5 and total). The number of TEAEs per 100 patients-years is calculated as the number of events

\*100 / (sum of the treatment emergent period duration of all patients treated in the corresponding treatment group, in years).

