Thrombocytopenia	Preferred terms of 'Thrombocytopenia', 'Platelet count decreased'			
Musculoskeletal events	Preferred terms of 'Back pain', 'Arthralgia', 'Myalgia', 'Musculoskeletal			
	pain', 'Pain in extremity', 'Musculoskeletal stiffness', 'Muscular			
	weakness', 'Muscle spasms'			
Severe cutaneous adverse	Narrow SMQ of 'Severe cutaneous adverse reactions'			
reactions (SCAR)				
Angioedema	Narrow SMQ of 'Angioedema'			
Rash	Preferred terms of 'Butterfly rash', 'Exfoliative rash', 'Eyelid rash',			
	'Genital rash', 'Heliotrope rash', 'Mucocutaneous rash', 'Nodular rash',			
	'Paraneoplastic rash', 'Penile rash', 'Perineal rash', 'Rash', 'Rash			
	erythematous', 'Rash follicular', 'Rash macular', 'Rash maculo-papular',			
	'Rash maculovesicular', 'Rash morbilliform', 'Rash neonatal', 'Rash			
	papular', 'Rash papulosquamous', 'Rash pruritic', 'Rash pustular', 'Rash			
	rubelliform', 'Rash scarlatiniform', 'Rash vesicular', 'Septic rash',			
	'Systemic lupus erythematosus rash', 'Vasculitic rash', 'Viral rash',			
	'Vulvovaginal rash'			
Hepatic disorder	Narrow SMQs of 'hepatic failure, fibrosis and cirrhosis and other liver			
	damage related conditions', 'hepatitis, non-infectious' and 'liver related			
	investigations, signs and symptoms'			

An overview table of the TEAEs of special interest will be described by the number and percentage of patients with TEAEs of special interest per treatment group and overall.

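### SAP 7.5.1 summarises special-interest adverse events at category level only as crude patient percentages, although the Enzalutamide and Placebo groups are observed over different periods

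*SAP*

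**What the plan says.** **Category-level output.** Table 3 of the SAP defines 19 special-interest categories. The overview table for them "will be described by the number and percentage of patients with TEAEs of special interest per treatment group and overall".

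**Observation periods (SAP 6.3).** One definition reads "Enzalutamide group: from the first DBT study drug intake up to 30 days after the date of the last dose of study drug", with earlier stops for study discontinuation or new antineoplastic therapy but none at entry to the extension. The Placebo group runs from the first double-blind dose "up to 30 days after the date of the last dose of placebo, start of open-label enzalutamide, study discontinuation" or new antineoplastic therapy, taking the earliest. Time on enzalutamide after crossover goes to a separate Placebo crossover group. SAP 7.3.1 plans exposure milestones out to year 4.

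**Duration-adjusted output (SAP 7.5.1).** There are two, both at term level:
- "To adjust for the treatment duration, the number of TEAEs per 100 patients-years will be summarized, as classified by SOC and PT", by group and by grade, with the summed treatment-emergent time of the group as denominator. This table has no frequency cut-off.
- A time-interval table by preferred term, limited by this rule: "The number and percentage of patients with TEAEs that equal to or exceed a threshold of 5.0% in any treatment group".

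SAP 7.3.1 also describes exposure by group. SAP 3.1 states the safety objective as a comparison with placebo plus ADT.

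**The concern.** A percentage of patients with at least one event grows with the time each patient is watched. When one group is followed through the extension and the other is cut at crossover, the two percentages can differ even if the drug has no effect. Placed side by side under a placebo-comparison objective, they invite a comparison that they cannot support.

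The categories matter clinically. Protocol 1.4 says "there are 4 important identified risks associated with enzalutamide (seizure, fall, nonpathological fracture and ischemic heart disease"). Fall is a single preferred term, so the term-level rate table covers it. The other three (seizure, nonpathological fracture and ischemic heart disease) sit in multi-term categories that have only a crude percentage at category level.

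Protocol 1.3 gives a reason to take duration seriously. Of 14 common TEAEs, all but nausea and pain in extremity (14 − 2 = 12) had a crude incidence at least 2% above placebo, yet "Only 2 TEAEs showed a higher rate in the enzalutamide vs the placebo group (event rate per 100 patient-years of treatment").

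**Working it through.** No sample size, power or alpha bears on this point, so there is no planned figure to reproduce.

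**1. Count the categories (SAP Table 3).**
- Total: 19. Single preferred terms: PRES and Fall. Multi-term: 19 − 2 = 17.
- Defined through an SMQ, HLGT or HLT: convulsions, hypertension, cognitive and memory impairment, ischemic heart disease, other cardiovascular events, renal disorder, second primary malignancies, fracture, severe cutaneous reactions, angioedema, hepatic disorder = 11.
- Defined by listed preferred terms: neutrophil count decreased, fatigue, loss of consciousness, thrombocytopenia, musculoskeletal events, rash = 6. Check: 11 + 6 = 17.

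**2. Size of the crude distortion under no true difference.** Exposure by arm is not in the documents, so every input here is an assumption: the same constant event hazard h in both arms (0.02 to 0.10 per year), a discontinuation hazard d = 0.30 per year in both arms, and a common cut-off T within each arm (1 to 2 years on placebo, 3 to 4.5 years on enzalutamide). Staggered entry and the 30-day tail are ignored.

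Crude incidence = h/(h+d) × (1 − exp(−(h+d)T)).

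Example at h = 0.05: for T = 1, 0.05/0.35 × (1 − e^−0.35) = 4.2%; for T = 4.5, 0.05/0.35 × (1 − e^−1.575) = 11.3%; ratio 2.69.

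| h per 100 patient-years | T = 1 | T = 2 | T = 3 | T = 4.5 | Ratio, enzalutamide to placebo |
|---|---|---|---|---|---|
| 2 | 1.7% | 2.9% | 3.9% | 4.8% | 1.31 to 2.79 |
| 5 | 4.2% | 7.2% | 9.3% | 11.3% | 1.29 to 2.69 |
| 10 | 8.2% | 13.8% | 17.5% | 20.9% | 1.27 to 2.53 |

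Over the same hazards, d = 0.20 gives 1.32 to 3.18 and d = 0.40 gives 1.23 to 2.48. Other assumptions move the range. Taking the design medians for rPFS (20 and 30 months, Protocol 7.1) as a proxy for time on treatment, with no crossover cut, h = 0.05 gives 10.7% against 15.3%, a ratio of about 1.4. Fixed observation of 1 against 4 years at h = 0.01 gives 1.0% against 3.9%, a ratio of 3.94. In all these cases the expected event-rate ratio is 1.

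**3. Would the interval table show it?** With d = 0.30 and T = 4.5, a preferred term needs h of about 0.021 to reach 5.0%. If a category with h = 0.05 were spread evenly over three terms, each would reach 4.0%, against 11.3% for the category, and none would enter that table. The patient-year table has no threshold and would show all three.

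**4. Do rates solve it fully?** Not if the hazard changes over time. Take 0.20 per year for 6 months, then 0.02, with d = 0.30:

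Rate = [0.20(1 − e^−0.15) + 0.02(e^−0.15 − e^−0.30T)] / (1 − e^−0.30T).

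This gives 11.67, 7.56, 6.23 and 5.38 per 100 patient-years at T = 1, 2, 3 and 4.5. With identical hazards the enzalutamide-to-placebo rate ratio runs from 0.46 (4.5 against 1 year) to 0.82 (3 against 2 years).

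**5. Does restricting to the double-blind period solve it?** SAP 6.3 uses one definition for both arms ("The double-blind treatment emergent period is defined as the time interval from the first double-blind study drug intake up to 30 days", with the same earlier stops), but one definition does not give equal exposure. Using the 20 and 30 month medians as a proxy, d = ln2/(20/12) = 0.416 on placebo and ln2/(30/12) = 0.277 on enzalutamide. At h = 0.05 a cut at 1.5 years gives 5.4% against 5.9% (ratio 1.10), and a cut at 2 years gives 6.5% against 7.3% (ratio 1.13). The gap is much smaller, but rates are still needed beside the percentages.

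**The case against.** The strongest reply is that the plan already adjusts for duration where it counts. The patient-year table covers every preferred term, with no cut-off. Its rows share one denominator within a group, so adding the right rows rebuilds a category event rate. Table 3 names each grouping and the SAP fixes MedDRA v23.0, so the sum is reproducible. Exposure is shown by group and all AEs are listed. On this view only a subtotal row is missing.

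Much of that stands. A reader might infer that special-interest events get no duration adjustment at all. That is not so: their component terms do. What remains is that the plan does not form the category rate. For 11 categories the reader would need the MedDRA lists, and the sum counts events while the planned table counts patients.

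Three further limits also stand:
- A reader might infer that no adjusted special-interest output exists anywhere. The documents do not support that. This SAP supplements SAP version 3.0 and leaves table layouts to TLF specifications, and neither is provided.
- A reader might take Protocol 1.3 as proof of a duration effect. It is consistent with one but does not isolate it. It sets patient incidence, with a 2% margin, against event rates, so the numerator changes as well as the denominator, and it pools five trials.
- The longer enzalutamide period is deliberate. Protocol 12.6.7 asks for a combined double-blind and open-label enzalutamide summary and treats extension data descriptively. The period itself is not an error; the unadjusted side-by-side display is the weakness.

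**Conclusion.** The point holds as a reporting gap in the text of this SAP. For 17 of 19 special-interest categories the only category-level summary is a crude patient percentage, over periods that SAP 6.3 defines differently for the two groups. With equal constant hazards of 2 to 10 per 100 patient-years, a discontinuation hazard of 0.30 per year, and 1 to 2 against 3 to 4.5 years of exposure, the crude ratio is about 1.3 to 2.8 with no true difference. A reader might take that range as the bias in this trial. It is not, because actual exposure by arm is not given and other assumptions shift the range.

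The table is descriptive, term-level rates are already planned, and no confirmatory conclusion changes. Priority is low to moderate.

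**What to change.** 1. For each Table 3 category and each group, add the number of events per 100 patient-years with the formula already in SAP 7.5.1.
2. Add a note that the cumulative crude percentages are not a between-group comparison.
3. Show the same categories for Enzalutamide and Placebo over the double-blind treatment-emergent period, with both percentages and rates. If SAP version 3.0 or the TLF specifications already contain this, a cross-reference is enough.
4. Optionally, add a first-event rate with a 95% CI.

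The cost is a few extra columns in a planned table, using a denominator that is already defined, and at most one extra descriptive display. The drawback is that rates can themselves mislead when the hazard is not constant, which is why the double-blind display belongs beside them.

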#### 7.5.2 Clinical Laboratory Evaluation

Laboratory assessment will be done for the following parameters:

Hematology	Biochemistry	Other	
Red blood cell count	Albumin	Testosterone	
White blood cell count	Alkaline phosphatase (ALP)	PSA	
White blood cell differential	Alanine aminotransferase (ALT)		
Hemoglobin	Aspartate aminotransferase (AST)		
Hematocrit	Blood urea nitrogen		
Platelet count	Calcium		
	Creatinine		
	Glucose		
	Phosphorus		
	Potassium		
	Sodium		
	Total bilirubin		
	Total protein		

Quantitative clinical laboratory variables (hematology, serum chemistry and testosterone), will be summarized using mean, standard deviation, minimum, maximum and median for Enzalutamide, Placebo and Placebo crossover group at each visit. Additionally, a within-patient change will be calculated as the post-baseline measurement minus the baseline

measurement and summarized in the same way. Baseline is defined as the last available measurement prior to the first dose (double-blind or open-label extension).

Based on the NCI-CTCAE grade of laboratory data, clinical laboratory evaluations will be summarized by grade and by visit, for their comparison to the upper limit. Shift analysis tables on the enzalutamide group will present the shift from baseline to each visit and to the highest grade among the post-baseline visits, by grade. The number and percentage of patients with an increase in grade will be summarized by visit.

Each laboratory result will also be classified as low (L), normal (N), or high (H) at each visit according to the laboratory supplied reference ranges.

Laboratory data will be displayed in listings, along with their NCI-CTCAE grade.

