When adjusted for treatment duration, the event rates for grade  $\geq$  3 TEAEs showed small differences ( $\leq$  1.2 events per 100 patient years) between the enzalutamide group and the placebo group.

Study drug-related TEAEs reported in  $\geq$  5% of patients in the enzalutamide group were fatigue (24.1% enzalutamide vs 14.1% placebo), hot flush (14.0% vs 8.7%), nausea (11.7% vs 10.4%), decreased appetite (8.2% vs 5.5%), asthenia (7.4% vs 4.4%), diarrhea (5.6% vs 4.4%) and hypertension (5.6% vs 2.0%).

The incidence of TEAEs leading to death was low in the pooled enzalutamide groups (4.8%) and in the placebo group (2.8%) and the adjusted event rates for serious TEAEs were also comparable in both groups.

The incidence of TEAEs leading to permanent discontinuation of study drug was similar in both groups; 17.2% in the pooled enzalutamide groups and 16.1% in the placebo group. The incidence of TEAEs leading to a dose reduction was 5.6% in the phase 3 enzalutamide group and 2.0% in the phase 3 placebo group. The incidence of TEAEs leading to a dosing interruption was 15.0% in the phase 3 enzalutamide group and 9.9% in the phase 3 placebo group

The pooled phase 3 safety data confirms that convulsion/seizure, cognitive and memory impairment, fatigue-related events, neutropenia/neutrophil count decreased, fall, fracture and hypertension are adverse events of special interest (AESI) for enzalutamide. Posterior reversible encephalopathy syndrome (PRES) is also considered an AESI for enzalutamide; however, this is based on cases reported during postapproval use of enzalutamide and not on events occurring in clinical studies.

Severe cutaneous adverse reactions, including acute generalized exanthematous pustulosis, dermatitis bullous, dermatitis exfoliative generalized, drug reaction with eosinophilia and systemic symptoms, erythema multiforme, exfoliative rash, Stevens-Johnson syndrome, toxic epidermal necrolysis and toxic skin eruption have been reported in post-marketing cases.

For more information on the investigational product enzalutamide and on the clinical study experience, refer to the current Investigator's Brochure of enzalutamide.

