# 5.5 Adverse Events and Other Safety Aspects

### **5.5.1** Definition of Adverse Events

An AE is defined as any untoward medical occurrence in a subject administered a study drug or has undergone study procedures and which does not necessarily have a causal relationship with this treatment. An AE can therefore be any unintended sign (including an abnormal laboratory finding), symptom, or disease temporally associated with the use of a medicinal (investigational) product, whether or not related to the medicinal (investigational) product.

Some countries may have additional local requirements for events that are required to be reported as AEs or in an expedited manner similar to a SAE. In these cases, it is the investigator's responsibility to ensure these AEs or other reporting requirements are followed and the information is appropriately recorded in the electronic case report form (eCRF) accordingly.

An abnormality identified during a medical test (e.g., laboratory parameter, vital sign, ECG data, physical examination) should be defined as an AE only if the abnormality meets 1 of the following criteria:

- Induces clinical signs or symptoms;
- Requires active intervention;
- Requires interruption or discontinuation of study medication;
- The abnormality or investigational value is clinically significant in the opinion of the investigator.

Clinical signs or symptoms of disease progression will be recorded as AEs. However, disease progression itself should not be recorded as an AE unless the disease progression results in death; this event is recorded as an AE with 'disease progression' as the reported term.

EudraCT number 2015-003869-28

- CONFIDENTIAL -

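### SAP 7.5.2 ties the laboratory summary by grade and visit to the upper limit, so no output is expressly specified to show, by treatment group, the low-direction grades reached

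*SAP*

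**What the plan says.** SAP 7.5.2 plans several laboratory outputs. The summary at issue is introduced with the words "clinical laboratory evaluations will be summarized by grade and by visit, for their comparison to the upper limit". The same paragraph adds two further summaries based on grade: "Shift analysis tables on the enzalutamide group will present the shift from baseline to each visit and to the highest grade", and "The number and percentage of patients with an increase in grade will be summarized by visit". Separately, "Each laboratory result will also be classified as low (L), normal (N), or high (H) at each visit", and "Laboratory data will be displayed in listings, along with their NCI-CTCAE grade". Ungraded values are "summarized using mean, standard deviation, minimum, maximum and median for Enzalutamide, Placebo and Placebo crossover group at each visit".

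SAP 7.5 sets the default that safety analyses are shown for all three groups unless a section says otherwise.

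Protocol 7.5 plans worst grades per subject for selected analytes, and summaries of grade 3 and 4 hematologic events by treatment group. Protocol 7.5.2 plans shift tables by CTCAE grade and also by reference-range indicator. Protocol 12.6.7 has extension laboratory values graded 1 through 4 where possible. None of these is limited to high values, and the shift tables in Protocol 7.5.2 are not limited to one arm.

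On neutrophils, Protocol 1.3 states that "neutropenia/neutrophil count decreased, fall, fracture and hypertension are adverse events of special interest (AESI) for enzalutamide". SAP Table 3 carries special-interest rows for decreased neutrophils and for thrombocytopenia.

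**The concern.** For neutrophils and platelets the direction of interest is downward. A summary that compares grades only with the upper limit does not show that direction. A programmer who follows the sentence as written would produce a grade-by-visit table without low neutrophil or platelet grades, for analytes whose low values the plan itself treats as of special interest.

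At stake is whether the report lets a reader compare enzalutamide, placebo and crossover patients on how severe the measured low counts became. Adverse event tables answer a different question. Under Protocol 5.5.1 an abnormal test result "should be defined as an AE only if the abnormality meets 1 of the following criteria", and those criteria involve clinical consequences, an intervention, a change to study medication, or the investigator's view of clinical significance. Values that meet none of them reach the report only through the laboratory outputs.

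**Working it through.** No arithmetic applies: the point depends on no alpha, power, effect size or event count. The check is to take each output in SAP 7.5.1 and 7.5.2 and ask three things. Is it based on grade? Is it open to low values? Does it show the grade reached in each treatment group?

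1. **Grade by visit.** Based on grade, and covers all groups by the SAP 7.5 default. Its wording is tied to the upper limit, so on a literal reading low grades are not shown.
2. **Grade shift tables.** Based on grade, no direction limit, and they show the grade reached. They are specified for the enzalutamide group, which overrides the three-group default and leaves no comparator. SAP 6.3 treats Placebo crossover as a separate group, so patients who first receive enzalutamide in the extension have no specified grade shift table either. Protocol 7.5.2 has no such restriction.
3. **Increase in grade by visit.** Based on grade, no direction limit, and it falls under the three-group default. It counts patients whose grade rose. A move from grade 1 to 2 counts the same as a move from grade 1 to 4, and for an analyte graded in both directions a rise on the high side is not separated from one on the low side.
4. **Low/normal/high classification.** Open to low values but ungraded. SAP 7.5.2 classifies each result but specifies no table of the classification, although Protocol 7.5.2 plans a shift by reference-range indicator.
5. **Descriptive statistics.** By group and visit, including the minimum. A minimum is one extreme value with no patient count and no grade.
6. **Listings.** They carry the grade for every result, but they are not summaries by group.
7. **Adverse event tables.** By group, with grade 3 or higher and maximum-severity summaries (SAP 7.5.1) and the special-interest overview. They depend on the investigator having recorded the abnormality as an adverse event.

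Result: of the three grade-based summaries (items 1 to 3), one carries the upper-limit wording and two do not. Of those two, one lacks comparator groups and the other lacks the grade reached and its direction. No output is expressly specified as a table, by treatment group, of low-direction laboratory grades.

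**The case against.** The strongest reply is that low values are far from absent. The increase-in-grade summary is a between-group output based on grade with no direction limit. The shift tables also have none. Protocol 7.5.2 requires clinically significant abnormal laboratory values to be recorded and graded as adverse events, so the values outside that route are mainly those judged not clinically significant and meeting no other criterion. This SAP is also a supplement to the main-study SAP (version 3.0), and table layouts sit in separate specifications; neither document is available here. Finally, the phrase may be loose drafting, since a strict upper-limit reading would leave little or nothing to tabulate for an analyte graded only on low values.

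Most of this stands, and it limits the point. A reader might infer that graded results are summarized only against the upper limit, or that low-direction toxicity is missing from the grade tables altogether. The documents do not support that, because two of the three grade-based summaries have no direction limit. A reader might also infer that neutropenia is one of enzalutamide's established risks. Protocol 1.3 names it an adverse event of special interest, but it is not among the four important identified risks in Protocol 1.4.

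What does not stand is that these outputs make the wording harmless. None of them is specified to show low grades reached, by group, from measured values. If the phrase is loose drafting, it still tells the programmer to produce the wrong table.

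**Conclusion.** The point holds in a limited form. The grade-by-visit summary in SAP 7.5.2, taken literally, omits low-direction grades. The remaining outputs reduce the gap without closing it, and the SAP is narrower than Protocol 7.5 and 7.5.2 without giving a reason.

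The size is modest: one summary and one restriction on the shift tables, in descriptive safety reporting. There is no effect on the overall survival test or its power.

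The conclusion rests on three assumptions. The sentence is applied as written. CTCAE v4.03 grades decreases in neutrophils and platelets; the documents do not reproduce its criteria, so no count of affected analytes is offered, and the argument relies on these two alone. The main-study SAP and the table specifications do not already supply the missing table, which cannot be checked from these documents.

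**What to change.** In SAP 7.5.2, replace the upper-limit phrase so that laboratory evaluations are summarized by grade and visit *in each direction CTCAE v4.03 defines, with high and low grades of the same analyte tabulated separately*. State that this summary and the grade shift tables are presented for Enzalutamide, Placebo and Placebo crossover, in line with Protocol 7.5 and 7.5.2.

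The cost is a change of wording and some more table rows. The values are already collected, and the listings already carry their grades, so no new data are needed.
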